#### **STUDY SPONSORSHIP**

- 1. Funding Sponsor:** Brain and Behavior Change Center (BBCC)

#### **PROTOCOL ABSTRACT**

Attention Deficit Hyperactivity Disorder (ADHD) is characterized by symptoms of impulsivity, inattention, and hyperactivity that emerge in childhood and frequently persist into adulthood. These symptoms are accompanied by deficits in cognitive control and risky decision making that can lead to negative psychosocial and health-related outcomes. With advances in the neuroimaging field, we are learning where and how self-control over decisions and behaviors is executed in the brain. This work points to the central role of neural activity in the dorsolateral prefrontal cortices (DLPFC) in self-control processes that contribute to healthy choices. Further, emerging evidence shows that activity in the prefrontal cortices and cognitive control circuits can be modulated using a noninvasive and safe intervention: repetitive transcranial magnetic stimulation (TMS). This within-subject proof of concept study will investigate whether 20 sessions of TMS (versus sham stimulation) can enhance executive cognitive function in adults with ADHD.

#### **OBJECTIVES**

##### **1. Overall Objectives**

**Aim 1:** To assess the effects of TMS (versus sham stimulation) on clinical measures of ADHD symptoms.

**Hypothesis:** Active TMS will reduce symptoms of ADHD as compared to sham treatment.

**Aim 2:** To assess the effects of TMS (versus sham stimulation) on cognitive performance and risk seeking in adults with ADHD.

**Hypothesis:** TMS treatment will improve cognitive performance and reduce risk seeking compared to sham treatment.

#### **BACKGROUND**

Attention Deficit Hyperactivity Disorder is a condition characterized by symptoms of impulsivity, inattention, and hyperactivity that emerge in childhood; in approximately 60% of cases these symptoms persist into adulthood where they may lead to challenges at work and at home (DSM-V, 2012; Faraone et al., 2006; Klein et al., 2012; Volkow and Swanson, 2013). Current pharmacological treatments include stimulants such as methylphenidate and amphetamine as well as atomoxetine, a norepinephrine transporter blocker (Sharma and Couture, 2014; Weyandt et al., 2014). Although these medications can provide relief from symptoms, they are not effective for all participants and require careful dose adjustment to minimize side effects while retaining clinical

benefits (Epstein et al., 2014; Sharma and Couture, 2014). There is a clear need for novel treatments for adult ADHD.

Inattention and impulsivity symptoms in adult ADHD are frequently accompanied by deficits in cognitive control and decision making (Aarts et al., 2015; Matthies et al., 2012; Mowinckel et al., 2014; Rohlf et al., 2012). These deficits are associated with reduced activity in regions subserving the executive control network, including the dorsolateral prefrontal cortex (Bush, 2011) (Bush 2011). Emerging evidence shows that activity in the prefrontal cortices and cognitive control circuits can be modulated using cognitive-enhancing medications (Ashare et al., 2012; Loughhead et al., 2010), computerized cognitive exercise training (Jaeggi et al., 2011; Snowball et al., 2013), and transcranial magnetic stimulation (TMS; (Brevet-Aeby et al., 2016)).

TMS is a non-invasive and relatively safe neuromodulation technique that uses Faradays' principle of electromagnetic induction. With TMS, repetitive magnetic pulses are applied to the scalp to generate electrical currents and depolarization of neurons in the targeted brain cortex with action potentials that propagate to subcortical structures and exert biological effects effect beyond the duration of stimulation. Currently, TMS is FDA approved for treatment of treatment resistant major depression. High frequency TMS delivered to the left dorsolateral prefrontal cortex has been used to treat depression (Garcia-Toro et al., 2001) and a number of other psychiatric disorders (Bystritsky et al., 2008; Clark et al., 2015; Del Felice et al., 2016; Dougall et al., 2015; Slotema et al., 2010; White and Tavakoli, 2015). In addition, a growing body of evidence supports the safety and potential utility of TMS for improving executive cognitive function (e.g. working memory) in healthy adults (Brevet-Aeby et al., 2016; Demirtas-Tatlidede et al., 2013). This has led to increased interest in TMS for improving executive function deficit in ADHD populations. To date, only a few studies have examined TMS protocols for treatment of ADHD, but initial evidence is promising (Bloch et al., 2010; Weaver et al., 2012; Zaman, 2015).

This within-subject proof of concept study will investigate whether repeated sessions of TMS (versus sham stimulation) can attenuate ADHD symptoms in adults.

## **CHARACTERISTICS OF THE STUDY POPULATION**

### ***1. Target Population***

95 healthy adults with ADHD between the ages of 18-65 will be enrolled in order to have 30 participants complete the study. Adults with ADHD are defined as those adults meeting diagnostic criteria for ADHD on the SCID-5 module for adult ADHD.

### ***2. Accrual***

95 male or female participants will be enrolled/sign consent to have 30 complete the study at the University of Pennsylvania Center for Interdisciplinary Research on Nicotine Addiction (CIRNA). Accounting for attrition based upon our previous studies on ADHD & tDCS, we estimate we will need to enroll 95 participants, 75 of which are projected to be eligible at intake, (~4-5 per month over a 22 month period) to have up to 30 participants complete the study. Participants will first be screened over the telephone and then complete an in-person Intake Visit with the Adult ADHD Treatment and Research Program or Center for Interdisciplinary Research on Nicotine Addictions to confirm final eligibility.

### ***3. Key Inclusion Criteria***

Eligible participants will be:

1. Healthy males and females who are between 18 and 65 years of age with an ADHD diagnosis (meet diagnostic criteria for ADHD on the SCID-5 module for adult ADHD).
2. Planning to live in the area for at least the next 6 weeks;

3. Capable of giving written informed consent, which includes compliance with the requirements and restrictions listed in the combined consent and HIPAA form;
4. Able to communicate fluently in English (speaking, writing, and reading).

#### **4. Key Exclusion Criteria**

Subjects who present and/or self-report with the following criteria at any point during study participation will not be eligible to participate in the study:

##### Alcohol/Drugs:

1. History or current diagnosis or treatment for alcohol or drug abuse (as reported during phone screen);
2. Positive breath alcohol concentration test (BrAC greater than or equal to 0.01) at intake;
  - a. Participants testing positive for breath alcohol with a reading equal to or greater than .08 (the legal driving limit) or who are visibly impaired will be instructed not to drive themselves home after the appointment. If a participant needs to use a phone to call for a safe ride home, an office telephone will be made available to the participant.
3. A positive urine drug screen for cocaine, PCP, amphetamines, methamphetamines, benzodiazepines, methadone, and/or barbiturates at Intake, Baseline, or Sessions 5, 10, 15 or 20.
  - a. Participants who are patients of investigators at the Penn Adult ADHD Treatment & Research Program who present a positive urine drug screen for amphetamines or methamphetamines at intake and report use of stimulant medications for the treatment of ADHD will be allowed to continue with participation.

##### Medication:

Current use or recent discontinuation (within the past 6 months at the time of Intake) of:

1. GABAergic medications
2. Glutamatergic medications
3. Any medication for the treatment of ADHD
  - a. Patients seeing investigators at the Penn Adult ADHD Treatment & Research Program for the treatment of ADHD will be given the option to abstain from their ADHD medication for the duration of the study. Since investigators at the Penn Adult ADHD Treatment & Research Program are part of the study team, they are able to oversee the medical aspects of the participant's treatment.
4. Any medication that is known to lower the seizure threshold (e.g., clozapine, bupropion, tramadol, carbapenems, stimulants)
5. Any medication that could compromise participant safety as determined by the Principal Investigator and/or Study Physician

Current use or recent discontinuation (within the last 14 days at the time of Intake) of:

6. Anti-psychotic medications
7. Nicotine replacement therapy (NRT)

Daily use of:

8. Opiate-containing medications for chronic pain
9. Benzodiazepines

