### **1. Screening/Covariates:**

Adult ADHD Self-Report Scale (ASRS) – Screening version: The screening version of the Adult ADHD Self-Report Scale (ASRS) Version 1.1 is a 6-question scale designed to screen for adult ADHD in community samples. The ASRS was developed by a World Health Organization (WHO) work group in conjunction with the creation of the WHO World Mental Health (WMH) Survey Initiative version of the WHO Composite International Diagnostic Interview (WMH-CIDI). This will be administered at phone screen.

Urine Drug Screen: A urine sample will be collected at Intake, Baseline and Sessions 1, 5, 10, 15 and 20 to conduct a urine drug screen. The urine drug screen indicates whether the subject has recently taken any of the following drugs or medications: cocaine, PCP, amphetamines, methamphetamines, opiates, methadone, THC, and/or barbiturates. Participants with a positive urine drug screen for any substance listed above other than THC will be deemed ineligible. In an effort to remain CLIA-compliant, results from urine drug screening will not be shared with participants. Participants will be informed that the testing is for research purposes only and that they will be informed of their eligibility status, but not of the specific testing results.

Urine Pregnancy Test: At the Intake and once a week during the study (Baseline & TMS Sessions 1, 5, 10, & 15), participants will be supplied with a simple, CLIA-waived urine pregnancy screen and informed that pregnant women are not advised to participate in this research study. Participants will then be instructed to administer the pregnancy test independently and will inform study staff if they would like to continue participation after they have administered the pregnancy screen. Participants will be informed that there is no penalty for discontinuing participation at this point in the visit and that they will still receive travel reimbursement for the visit.

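### Eligibility rules contradict each other for Penn ADHD-program patients on, or stopping, a prescribed stimulant: one criterion excludes them without exception and two exceptions let them in

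*Combined protocol and SAP*

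**What the plan says.** All references are to the combined protocol and SAP.

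- **Key Exclusion Criteria, lead-in.** Anyone who meets a listed criterion "at any point during study participation will not be eligible to participate in the study".
- **Medication, items 1 to 5.** The lead-in reads "Current use or recent discontinuation (within the past 6 months at the time of Intake) of". Item 3 is any ADHD medication. Under it, item 3a says that patients of the Penn Adult ADHD program investigators "will be given the option to abstain from their ADHD medication for the duration of the study". Item 4 is a separate criterion: "Any medication that is known to lower the seizure threshold (e.g., clozapine, bupropion, tramadol, carbapenems, stimulants". It has no sub-item.
- **Alcohol/Drugs, item 3a.** Patients of the same investigators who are positive for amphetamines or methamphetamines at Intake and "report use of stimulant medications for the treatment of ADHD will be allowed to continue with participation".
- **Screening/Covariates, Urine Drug Screen.** Amphetamines and methamphetamines are on the panel, and the rule is "Participants with a positive urine drug screen for any substance listed above other than THC will be deemed ineligible".
- **Procedures, Intake item 2.** Exclusionary positives make a participant ineligible; the text refers back to the exclusion criteria.
- **Active TMS.** The exclusion of patients who are taking threshold-lowering drugs is offered as an added safety margin for the stimulation settings.
- **Potential Study Risks, Withdrawal Syndrome.** Symptoms after stopping stimulants are listed as a risk of the study.

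**The concern.** Recruitment draws on the Adult ADHD Treatment and Research Program, so program patients on prescribed stimulants are a group that the study can expect to meet at Intake. For them, a coordinator working from the two exceptions would proceed, and one working from Medication item 4 would exclude. Item 4 is a seizure-related criterion, the risk section calls seizure the most significant TMS risk, and the Active TMS section cites the exclusion of patients taking such drugs in support of its settings. A rule with that purpose should give one answer for a given patient. If it does not, eligibility decisions may differ between staff, and it will be unclear afterwards which enrolments were protocol deviations.

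**Working it through.** The plan gives no figure to reproduce here. The check is to apply each rule to defined patients, all of them patients of the program investigators.

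**Patient A: on prescribed amphetamine at Intake, screen positive, reports the prescription, agrees to abstain.**
- Alcohol/Drugs item 3a: may continue.
- Medication item 3 with 3a: may take part by abstaining. This admits by implication; the text offers an option and does not say in terms that the patient is eligible.
- Medication item 4: excluded, as a current user of a stimulant at Intake. Abstaining afterwards does not change that status.
- Screening/Covariates: ineligible as worded, because only THC is exempted.

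**Patient B: stopped a stimulant in order to join, within 6 months before Intake, screen negative.**
- Alcohol/Drugs item 3a: not triggered.
- Medication item 3a: may take part by abstaining.
- Medication item 4: excluded by the look-back.

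**Patient C: on an ADHD drug that is not a stimulant.** The Background describes atomoxetine separately from the stimulants. On the assumption that such a drug is not otherwise judged to lower the seizure threshold, item 3a lifts item 3 and item 4 is silent. There is no conflict.

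**Patient D: admitted at Intake, then amphetamine-positive at Baseline or at Session 5, 10, 15 or 20.** The Alcohol/Drugs exception is confined to Intake, so the patient is excluded. There is no conflict.

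Two things follow. First, Medication item 3a has work to do without touching item 4 (patient C), so an implied override of item 4 cannot be read out of it. Second, Alcohol/Drugs item 3a concerns only people who report stimulant treatment and have just screened positive. Each of them is a current user or a recent discontinuer at Intake, so item 4 as written excludes every patient whom that exception is meant to keep. The Withdrawal Syndrome text fits a plan that expects such patients to enrol.

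**Visit lists.** The Alcohol/Drugs criterion ends with "barbiturates at Intake, Baseline, or Sessions 5, 10, 15 or 20": Intake, Baseline and four sessions, 2 + 4 = 6 visits. Screening/Covariates says "A urine sample will be collected at Intake, Baseline and Sessions 1, 5, 10, 15 and 20 to conduct a urine drug screen": 2 + 5 = 7 visits. The difference, 7 − 6 = 1, is Session 1. The TMS Sessions procedures also screen at Session 1, but refer staff back to the Alcohol/Drugs criterion, which does not say what a Session 1 positive means.

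**The case against.** The best reply is that the documents largely agree on what matters most for safety, namely stimulant use while stimulation is given. Medication items 3 and 4 bar current use, and the exclusions apply throughout participation. The urine exception ends at Intake, medication changes are asked about at Baseline and at Sessions 1, 5, 10, 15 and 20, and the TMS Safety Checklist re-checks eligibility at every session. The Active TMS statement concerns patients who are taking such drugs and invokes no look-back. This stands. A reader might infer that the plan permits stimulation of patients on stimulants, or that its stated safety margin is breached; the documents do not support either.

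A second reply is that the urine-screen rule in Screening/Covariates is a general summary, which the specific exception in the formal criteria qualifies. That is a fair reading, and the Intake procedures point the same way by referring to the criteria. It makes the missing exception there a secondary wording fault. It does nothing for item 4, which is a medication criterion and not a urine-screen rule.

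A third is that abstaining is plainly the price of entry. That is the natural sense of item 3a, but it answers item 3 only; a patient who stops in order to join still falls under item 4.

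The visit mismatch might suggest that Session 1 goes unscreened. It does not: both the procedures and Screening/Covariates collect urine there. It is a discrepancy between lists and adds no weight to the main point.

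**Conclusion.** The contradiction is real and should be resolved. Medication item 4 excludes program patients who use a stimulant, or who stopped one within 6 months before Intake, while Medication item 3a and Alcohol/Drugs item 3a provide for their participation. Nothing in the text says which prevails. The practical core is item 4's look-back for recent discontinuation, not current use during stimulation.

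This rests on reading item 3a as attached to item 3 alone, as its placement shows, and on treating each listed criterion as disqualifying in its own right, as the lead-in states. How many patients are affected, and any effect on the results, cannot be computed from the documents.

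**What to change.** Reconcile the Alcohol/Drugs and Medication exclusions, the Intake and TMS Sessions procedures, and the Urine Drug Screen text in Screening/Covariates into one eligibility rule for these patients.

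1. State whether the option in Medication item 3a and the exception in Alcohol/Drugs item 3a also apply to Medication item 4 and its 6-month window.
2. If an exception is retained, word it identically wherever the urine-screen rule appears. If it is not, remove it.
3. Check that the safety statement under Active TMS and the Withdrawal Syndrome text match the resulting rule.
4. In the same amendment, align the list of exclusionary screen visits and say whether Session 1 counts.

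Which clinical rule applies is for the investigators and the IRB. The cost is amendment wording and IRB review; no new visit, assay or measure is needed.

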##### Medical/Neuropsychiatric:

1. Women who are pregnant, planning a pregnancy, and/or breast feeding. Women of childbearing potential will agree to use a medically accepted method of birth control throughout their participation in the study and will undergo a urine pregnancy test once a week (at intake, Baseline, Session 1, Session 5, Session 10, & Session 15). Women who self-report a condition which renders them unable to become pregnant (i.e.,

hysterectomy, surgical sterility, menopause, etc) will not be required to complete the pregnancy tests. By enrolling in this protocol women of childbearing potential agree to use a method of medically accepted birth control (diaphragm, cervical cap, condom and spermicide, surgical sterility, or birth control pills) for the duration of their participation.

2. History of seizures, epilepsy, or history of epilepsy in first-degree relative
3. History of stroke or transient ischemic attack (warning stroke)
4. History of traumatic brain injury or self-report of brain or spinal tumor
5. History of head injury with unconsciousness lasting more than 5 minutes
6. Previous brain surgery
7. Any additional neurological condition that would likely reduce the safety of study participation, including central nervous system (CNS) vasculitis, intracranial tumor, intracranial aneurysm, multiple sclerosis or arteriovenous malformations
8. History of tinnitus
9. History of diabetes mellitus
10. History of atherosclerotic vascular disease
11. A medically unstable cardiopulmonary or metabolic disorder
12. Increased risk for myocardial infarction or other major cardiopulmonary complications. (Exclusions include, but are not limited to, subjects with unstable angina, decompensated congestive heart failure, severe cardiac valvular disease, a high-grade atrio-ventricular block on EKG, or a symptomatic ventricular arrhythmia or a myocardial infarction within 6 months prior to enrollment.)
13. Any uncorrected visual impairment or abnormality
14. Self-reported history, current diagnosis of psychosis or symptoms consistent with a mood disorder based upon the Structured Clinical Interview for DSM-5 (SCID); including schizophrenia, mania, bipolar disorder, an eating disorder, obsessive compulsive disorder, major depression (subjects with a history of major depression but in remission for past 6 months are eligible). If a participant screens positive for one of the above mentioned mood or depressive disorders they will be excluded from the study and provided with contact information for local treatment programs (mood referrals document).

TMS-related:

1. Subjects with ferromagnetic material in or in close proximity to the head (with the exception of oral dental devices).
2. Implanted devices (including VNS, DBS, pacemakers, spinal cord stimulators, medication pumps, ventriculo peritoneal shunts, defibrillators, intracardiac lines)
3. Self-report of any skull fracture or opening
4. A disturbance in normal sleep patterns/sleep deprivation

Note: Although there is no known risk of TMS to the fetus, the issue has not been fully addressed. Consequently, pregnant women will be excluded. All women of childbearing potential (as described above) will agree to use a medically accepted method of birth control while enrolled in the study and pregnancy status will be monitored throughout participation with the use of pregnancy screens.

General Exclusion:

1. Any medical condition, illness, disorder, or concomitant medication that could compromise participant safety or treatment, or affect clinical or cognitive outcomes, as determined by the Principal Investigator
2. Inability to complete study tasks and provide quality data, as determined by the Principal Investigator

3. Low or borderline intellectual functioning – determined by a score of less than 90 on the Shipley Institute of Living Scale (SILS) (administered at Intake Visit). The SILS correlates with the Wechsler Adult Intelligence Scale-Revised (WAIS-R) Estimated IQ Test
4. Inability to provide informed consent

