### **2. Design**

This trial will use a between-subject double blind design in which TMS dosage (active or sham) will be randomly assigned. Eligible participants will complete an **Intake Visit (week 0)** for final eligibility determination. Eligible participants will complete an additional 20 study visits

(5 visits per week for 4 consecutive weeks) during which they will receive 26-minute sessions of TMS. Participants will complete a series of computerized cognitive assessments prior to initiating the TMS period (Baseline) and will complete the same series of computerized cognitive assessments after their final TMS session (Session 20).

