3. BrAC assessment. See breath alcohol concentration under screening/covariates for exclusionary criteria;

4. Provide information regarding recent nicotine and caffeine intake, and any medication changes since the Intake visit;
5. A carbon monoxide (CO) breath sample (smokers only);
6. Complete paper and pencil questionnaires (POMS);
7. Complete computerized cognitive tasks which may include assessments of working memory, sustained attention, risk aversion, delay discounting or reaction time.

**TMS Sessions (Sessions 1 - 20):** (Visit duration ~1-2hrs). The stimulation protocol is adapted from TMS Investigations of Cognition and Motor Function, which was employed in The Laboratory for Cognition and Neural Stimulation (LCNS).

Participants will complete the following during Sessions 1 - 20:

1. Urine drug screen (Sessions 1, 5, 10, 15 & 20). See key exclusionary criteria; Alcohol/Drugs;
2. Pregnancy screen (females of child bearing potential only) (Sessions 1, 5, 10, 15 & 20);
3. BrAC assessment. See breath alcohol concentration under screening/covariates for exclusionary criteria;
4. Assessment of recent nicotine and caffeine intake, and any medication changes since last assessment (Sessions 1, 5, 10, 15 & 20);
5. TMS safety & side effects questionnaire;
6. A carbon monoxide (CO) breath sample (smokers only);
7. Complete paper and pencil questionnaires;
8. Receive 26 minutes of TMS (active or sham);
9. Complete computerized cognitive tasks which may include assessments of working memory, sustained attention, risk aversion, delay discounting or reaction time (Sessions 5, 10, 15 & 20).

**Attendance:** Participants will be asked to attend all study visits. Participants attending less than 4/5 visits during the first two weeks or less than 3/5 sessions in the final two weeks of the study will be excluded.

**TMS Training Procedures:** Prior to each TMS session an investigator or trained research assistant will review the procedures, goals, risks, and potential benefits of the study and confirm that no change has occurred affecting study inclusion and exclusion criteria. The TMS sessions will be conducted by a trained TMS clinician using the The MagPro R30 (Magventure, Inc., Copenhagen, Denmark) device with a figure 8 coil. During Sessions 1 - 20 participants will receive 26 minutes of sham or active TMS using the parameters described below. Participants will be blind to condition.

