## **2. Statistical Analysis**

**General Issues:** Prior to performing analyses, standard data screening/cleaning procedures will be applied. These procedures will (a) screen the data for data-entry errors, (b) check for outliers, (c) assess the extent and pattern of missing data, (d) create all summary scores needed for analysis, and (e) check that appropriate distributional assumptions are met. In all analyses, the assumptions underlying the application of all the statistical methods that are used will be examined, principally through the use of standardized residuals, influence diagnostics, and graphical displays. All analyses will be conducted using Stata software (STATA Corporation, College Station, Texas).

**Hypothesis Testing:** The primary outcomes will be cognitive performance on the tasks administered before and after TMS. All of these outcome measures are continuous, and hypotheses will be tested using mixed effects modeling. A sample size of 30 individuals will provide ~80% power to detect a moderate to large effect size, similar to the effect size seen for TMS treatment of depression.

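### The exclusion list lets the Principal Investigator remove randomised participants for poor-quality data on the tasks that are the Aim 2 outcomes, and no analysis set keeps them in

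*Combined protocol and SAP*

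**What the plan says.** Key Exclusion Criteria opens with a timing rule for the whole list: "Subjects who present and/or self-report with the following criteria at any point during study participation will not be eligible to participate in the study". General Exclusion item 2 then reads "Inability to complete study tasks and provide quality data, as determined by the Principal Investigator". It names no task, visit, threshold or procedure. Item 3, directly after it, gives both a score and a visit (SILS below 90, at Intake).

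Procedures and Table 1 place the computerized tasks at Baseline and at Sessions 5, 10, 15 and 20. Intake has none. Aim 2 is "To assess the effects of TMS (versus sham stimulation) on cognitive performance and risk seeking in adults with ADHD". Table 1 lists the PASAT, CPT and Risk Task as secondary outcomes, while Statistical Analysis says "The primary outcomes will be cognitive performance on the tasks administered before and after TMS". Background adds that "Inattention and impulsivity symptoms in adult ADHD are frequently accompanied by deficits in cognitive control and decision making".

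Statistical Analysis plans mixed effects models and a look at the extent and pattern of missing data. It defines no analysis set and gives no rule for the data of someone removed during the study. The Design section describes a randomised, double-blind, between-subject trial, and that is the design assumed here (the Abstract and Background call it within-subject). The time of randomisation is not stated.

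**The concern.** An exclusion rule is harmless to a randomised comparison while it acts before allocation. This one stays in force afterwards and rests on one person's judgement of data from the outcome tasks. A participant who drifts through the CPT or gives up on the PASAT could be recorded as a poor outcome or as poor-quality data, and the protocol does not say which.

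If the second label leads to removal and the data are then left out, retention depends on the endpoint. Should active TMS improve performance, more sham than active participants would fall short of a common standard, and the observed difference would shrink. If stimulation impaired performance, the impairment would be understated in the same way. If the standard were applied differently in the two arms, a difference could appear where none exists. The target is only 30 completers, so a few such decisions carry weight.

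**Working it through.** **The plan's own figure.** The plan gives no number for this rule. Its only related figure is about 80% power with 30 individuals, which cannot be reproduced because alpha, a numerical effect size and a within-person correlation are not given. It does not decide this point.

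**When the rule can act.** Five visits carry the task battery: Baseline and Sessions 5, 10, 15 and 20. Four of the five fall during treatment. If randomisation follows Baseline, only the Baseline battery can trigger the rule without affecting the comparison.

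**Worst case: one score, full deletion, common standard.** Assumptions, none from the documents: sham scores N(0, 1), active scores N(δ, 1), higher is better, and everyone below a common cut c is deleted. Here c = Φ⁻¹(q), where q is the share of sham removed.

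- Share of active removed: Φ(c − δ)
- Mean of those retained: μ + φ(c − μ) / [1 − Φ(c − μ)]

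With δ = 0.5 and q = 0.10, c = −1.2816:
- sham: 0 + 0.1755/0.90 = 0.195
- active: 3.7% removed; 0.5 + 0.0816/0.9626 = 0.585
- difference: 0.585 − 0.195 = 0.39 SD, or 78% of the true effect

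With δ = 0.5 and q = 0.20, c = −0.8416:
- sham: 0 + 0.2800/0.80 = 0.350
- active: 9.0% removed; 0.5 + 0.1622/0.9101 = 0.678
- difference: 0.678 − 0.350 = 0.33 SD, or 66% of the true effect

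With δ = 0.8 the same formulas leave 0.65 and 0.56 SD. In simulated two-sample t-tests (15 per arm and two-sided 0.05, both assumed), power at δ = 0.5 falls from 26% to 20% or 16%. At δ = 0.8 it falls from 56% to 45% or 37%.

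**Same rule, no true effect.** With δ = 0 the two retained means are equal for any q, so there is no bias, and the simulated type I error stays at 0.05.

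**Unequal removal, no true effect.** Dropping the 1, 2 or 3 lowest of 15 scores from the active arm only gives a false difference of about 0.13, 0.23 or 0.33 SD. Two-sided type I error becomes 0.070, 0.107 or 0.159.

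**Repeated scores kept in the model.** A further simulation used five visits, correlations of 0.5, 0.7 or 0.89, an effect rising linearly to 0.5 SD at Session 20, and removal after any score below the sham 5th or 10th percentile. The analysis was a saturated likelihood model.
- All observed scores kept, including the one that triggered removal: estimate about 0.50 with 8–22% of sham removed, so essentially no bias.
- Triggering score also discarded: about 0.42 to 0.49, or 84–98% of the true effect, with 9–26% of sham lost.

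**The case against.** The strongest reply is that item 2 is a feasibility criterion. It speaks of inability, sits beside screening-type items such as capacity to consent, and may cover questionnaires and session procedures as well as the three tasks. A valid low score is still data of adequate quality. Someone who cannot do the tasks may be found at Baseline, before any stimulation. The trial is called double blind and plans mixed models on repeated measures, and nothing says that a removed participant's earlier scores are thrown away.

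Much of this stands, and it rules out four stronger readings that a reader might infer:

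- **That the arms are in fact selected on the Aim 2 result.** The text permits this but does not show that it happens.
- **That the item is a score cut-off.** No threshold is stated or implied. The hard cut in the working is only a device for sizing the problem.
- **That the rule favours a false positive.** With a blind common standard and no true effect there is no bias. A spurious difference needs unequal removal, and the documents give no evidence of that.
- **That 66–78% is the expected size of the surviving effect.** Those figures need a single score and full deletion, and the planned repeated-measures model could avoid most or all of the loss.

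The reply does not remove the point. The opening line keeps the item in force throughout, and no wording separates quality from performance. The Principal Investigator's blinding rests on the double-blind label alone, because Procedures names only participants as blind. The protection offered by a mixed model depends on keeping the scores that prompted removal, which the plan does not promise. It would also weaken if the judgement rested on behaviour not captured in the data.

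**Conclusion.** The concern holds as a statement about what the rule allows. As written, the plan permits discretionary, outcome-related removal after randomisation, and no analysis set offsets it. This can bias the active-sham comparison on Aim 2, and on the primary outcome if the Statistical Analysis wording governs.

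The likely direction under a blind common standard is dilution of a true effect. For a true 0.5 SD the plausible range runs from almost no loss, if all observed scores enter a likelihood model, down to 0.39 or 0.33 SD in the worst case with 10% or 20% of sham removed. All of these figures rest on assumed normal scores and assumed removal rates. The plan should be corrected, but it does not show that the trial's result is compromised.

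**What to change.** - **Key Exclusion Criteria and General Exclusion item 2:** apply item 2 only before randomisation, judged on the Baseline battery, and exempt it from the clause that keeps criteria in force throughout. State when randomisation takes place, since the limit depends on it.
- **After randomisation:** do not remove a participant for poor or incomplete task performance. Score each run as obtained, with the scoring of unfinished runs set in advance. Discard a run only for equipment or administration failure that was recorded before the score was seen.
- **Statistical Analysis:** analyse all randomised participants, with all data collected from them, in the mixed model. Report any removals by arm, with reasons.

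The cost is a sentence or two in each of these places. The downside is somewhat noisier task data from a few participants. Safety-based exclusions are not touched.
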